5.1.3 Exploratory

- Time to maximum severity of COVID-19 symptoms after start of treatment
- Time to resolution of COVID-19 symptoms including cough, fever, shortness of breath and elevated respiratory rate
- Proportion of individuals clinically recovered at Day 28 [± 1 day]

5.2 Safety Endpoints

- Adverse events (AEs) and serious adverse events (SAEs) events
- Vital signs (respiratory rate, temperature, heart rate, blood pressure, O₂ saturation)
- New clinical symptoms of COVID-19 disease not present at screening
- Clinical chemistry and hematology

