-------------------------------	--

	
(4) Receipt of any experimental treatment for COVID-19 (off-label, compassionate use, or study-related) within the 30 days prior to the time of the screening evaluation(5) Any excluded concomitant medication as described in the ARAKODA package insert [Section 15.1](6) Any COVID-19 symptoms which, in the opinion of the investigator, is suggestive of possible requirement to hospitalize within 48 hours of enrollment(7) Positive pregnancy test(8) Have been symptomatic for more than five days when the first dose would be administered
Treatment Groups:	There will be 2 treatment groups; TQ and placebo for which at least 250 patients will be randomized in 1:1 ratio to treatment with clinical site as a stratification variable. Randomizations will continue until at least 250 patients meet the criteria for mITT.
Screening Procedures:	After signing informed consent, patients will be screened for eligibility including medical history, G6PD, RT-PCR for SARS-CoV-2, pregnancy testing for females of child-bearing potential, hematology, blood chemistry, vital signs, O ₂ saturation, and physical exams. The Screening period will be a maximum of 4 days (Days -4 to -1), and the first day of dosing will be Study Day 1.
Randomization Procedure:	Eligible patients will be randomized at a 1:1 ratio to receive TQ or placebo. Randomization will be performed through a centralized, web-based, validated system that automates the assignment of patients to treatment allocation. Randomization will be stratified by clinical site.
Efficacy Assessments:	
• Clinical signs and symptoms of COVID-19 (clinically diagnosed and patient reported) including fever, shortness of breath, cough, and respiratory rate daily from Day 1 to Day 28 (Note, the clinical signs of COVID-19 will not be reported as AEs)• SARS-CoV-2 PCR at Day 12 ± 1 day.• Hospitalization

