6.2 Schedule of Study Assessments

Table 1 Schedule of Procedures

Procedure	Screening Day -4 to -1	Day 1	Day 1	Days 2 and 3 ± 1 day	Days 4 to 9	Day 10 ± 1 day	Day 11	Day 12 ± 1 day	Day 28 ± 1 day
Clinic Visit #	1	If in clinic	If at home					2 or 3	
Informed consent	X								
Eligibility criteria	X	X	X						
Pregnancy testing ¹	X							X	
Demography	X								
Medical history	X	updated	updated						
G6PD test	X								
Physical exam	X							X	
Vital signs ²	X							X	
Clinical symptoms of COVID-19 ³									
Temperature ⁴	X	X	Self-measured by patient daily and recorded in eDiary					X	
Respiration rate ⁵	X	X	Self-measured by patient daily and recorded in eDiary						
Shortness of breath (severity scale) ⁶	X	X	Self-reported by patient daily and recorded in eDiary					X	
Cough (severity scale) ⁷	X	X	Self-reported by patient daily and recorded in eDiary					X	
Pulse oximetry for oxygen saturation	X	X	Self-measured by patient daily and recorded in eDiary					X	
Prior and concomitant medications ⁸	X	updated	Recorded by clinician at telemedicine visit					X	Recorded by clinician at telemedicine visit
Adverse events			Self-reported by patient and recorded in eDiary, and recorded during telemedicine visit including severity and relationship to study drug, plus actions taken to treat AE or if drug discontinued					X	Recorded by clinician at telemedicine visit

Procedure	Screening Day -4 to -1	Day 1	Day 1	Days 2 and 3 ± 1 day	Days 4 to 9	Day 10 ± 1 day	Day 11	Day 12 ± 1 day	Day 28 ± 1 day
Clinic Visit #	1	If in clinic	If at home					2 or 3	
RT-PCR	X							X	
Hematology ⁹	X							X	
Blood chemistry ¹⁰	X							X	
Randomization		X	X						
Load eDiary to Patient Device, provide pulse ox device, thermometer, and instructions for use		X	X						
Dispense study drug ¹¹		X	X						
Study drug administration			X	Each day		X			
Medication compliance			eDiary	eDiary		eDiary			
Final drug accountability								X	

¹ A serum pregnancy test will be performed at screening and a urine or serum pregnancy test will be performed at Day 12.

² Vital signs include blood pressure and heart rate

³ COVID-19 symptoms will be assessed by designated clinical staff at in-clinic visits and will be checked at home by the patients and reported by the patient in the electronic diary (eDiary). Once the data is recorded in the diary it will be uploaded to the study database for clinician review.

⁴ Temperatures will be taken orally or on the skin surface and recorded in degrees Centigrade.

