10.1.3.2 Adverse Event and Serious Adverse Event Reporting Procedures

- Safety Contact Information:

Drug Safety Navigator (DSN)

Email: [contact]

- AE Reporting:

AEs occurring (initial occurrence or a worsening of a pre-existing condition) after the subject signs the informed consent form and up to the final follow-up visit at Day 28 will be reported and included in the study database.

AEs will be reported on the AE CRF Form, and any related questions should be directed to DSN.

- SAE Reporting:

Any SAE experienced from the time the subject signs the informed consent up to the final follow-up visit at Day 28 will be reported to DSN as described below. Additionally, SAEs that occur after completion of the Follow-up period will also be reported to DSN if the Investigator considers the SAE related to study drug.

SAEs must be reported to DSN within 24 hours of the Investigator's (site's) awareness or notification of the event. To report the SAE, the site must complete the SAE Form for the study. This form is not part of the eCRF and will be provided separately to the Investigator by DSN. Initial and follow-up

SAE reports will be sent to DSN via email to [contact], and to the sponsor's Chief Medical Officer and to the Medical Monitor.

The SAE reporting should not be delayed, and the sites may call and provide the available SAE information within 24 hours of Investigator's awareness. A written SAE Form should be sent via email to [contact], as soon as possible.

The Investigators should make every effort to provide complete information on the SAE Form. At the minimum, the initial SAE report must contain the subject's identifiers, event term as known, SAE criterion and the Investigator's causality assessment. Additional information (or updates to the previously reported information) may be provided, as it becomes available through a follow-up SAE report.

The Investigator must continue to follow the subject until the SAE resolves, the condition becomes chronic in nature, stabilizes (in the case of persistent impairment), or the subject dies. Within 24 hours of receipt of follow-up information, the Investigator must complete the SAE Form and submit any supporting documentation, as necessary (e.g., laboratory test reports, subject discharge summary, or autopsy reports) to DSN via email to [contact].

The Investigator is also required to submit SAE reports to the IRB in accordance with applicable requirements.

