12.4 Planned Safety Analyses

12.4.1 Adverse Events

AEs will be coded using the most recent version of the Medical Dictionary of Regulatory Activities (MedDRA) preferred terms and will be grouped by system, organ, and class (SOC) designation. The incidence of new COVID-19 symptoms not present at screening will be reported separately from other AEs including the maximum severity and time of maximum severity relative to the start of investigational product. The severity, frequency, and relationship of AEs to investigational product will be presented by preferred term by SOC grouping. Listings of each individual AE including start

date, stop date, severity, relationship, outcome, and duration will be provided. Each AE (based on preferred terminology) will be counted once only for a given patient. If the same AE occurred on multiple occasions, the highest severity and relationship to investigational product will be assumed. Thus, study participants are not counted multiple times in a given numerator in the calculation of frequencies for a specific AE.

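### New COVID-19 symptoms are counted against screening rather than the Day 1 pre-dose assessment, so symptoms that start before any drug is taken dilute the comparison between arms

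*Combined protocol and SAP*

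**What the plan says.** Section 5.2 lists "New clinical symptoms of COVID-19 disease not present at screening" as a safety endpoint, and the synopsis has an equivalent entry. Section 12.4.1 carries the reference point into the analysis: the "incidence of new COVID-19 symptoms not present at screening will be reported separately from other AEs". The same sentence measures the time of maximum severity from the start of investigational product, so incidence and timing have different origins.

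The gap between screening and first dose is described in three ways. The synopsis, Section 6.1.1 and Table 1 place screening on Days -4 to -1, with dosing on Day 1. Section 6.1 has eligible patients randomized no more than two days after the screening visit. Section 9.2.2 repeats this and adds a 48-hour limit.

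Sections 7.1 and 7.2 require that symptoms have lasted no more than 5 days at first dose. One qualifying symptom is enough for entry. Table 1 schedules temperature, respiration rate, shortness of breath and cough at screening and again on Day 1. Its footnote 3 explains that "COVID-19 symptoms will be assessed by designated clinical staff at in-clinic visits and will be checked at home by the patients". The order of the Day 1 entry and the first dose is not stated.

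**The concern.** Patients are enrolled early, while their symptoms may still be evolving. Someone who enters with cough alone can develop fever or shortness of breath before the first tablet. Under the stated rule that symptom is new on study, although no study drug had been taken.

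The protocol draws its line at first dose elsewhere. Section 12.2.4 defines prior medications by the first dose, and Section 5.1.3 measures time to maximum severity from the start of treatment. The new-symptom endpoint does neither.

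The stake is the ability to see a difference. Events that occurred before dosing cannot reflect treatment. They raise the count in both arms, and they make a protective or a harmful effect look smaller than it is.

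**Working it through.** **Plan's own figure.** The documents give no event rate, effect size or power for this endpoint. The 125 per arm in Section 12.6 concerns Day 12 recovery and does not enter here.

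**Inputs**
- Reference point: screening (Sections 5.2 and 12.4.1).
- Gap to first dose: at most 4 days (synopsis, Section 6.1.1, Table 1), or 2 days (Sections 6.1 and 9.2.2, the latter with a 48-hour limit).
- Pre-dose rate q and after-dose rates p: not in the documents. The values below are assumptions, shown over a range.

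**Model.** Let q be the probability that a symptom first appears between screening and first dose. Randomization makes q the same in both arms in expectation. Let p be the probability that it first appears after dosing in a patient still free of it, independent of q. Each patient counts once.

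- Observed risk = q + (1-q)p
- Observed risk difference = (1-q)(p1 - p0)
- Observed risk ratio = [q + (1-q)p1] / [q + (1-q)p0]

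Worked case, p0 = 10% and p1 = 5%:
- q = 2%: (0.02 + 0.98 × 0.05) / (0.02 + 0.98 × 0.10) = 0.069 / 0.118 = 0.58
- q = 5%: (0.05 + 0.95 × 0.05) / (0.05 + 0.95 × 0.10) = 0.0975 / 0.145 = 0.67

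| After-dose rates | q | Observed risks | Risk difference (points) | Risk ratio |
|---|---|---|---|---|
| 10% vs 5% | 0 | 10.0% vs 5.0% | 5.00 | 0.50 |
| | 2% | 11.8% vs 6.9% | 4.90 | 0.58 |
| | 5% | 14.5% vs 9.75% | 4.75 | 0.67 |
| | 10% | 19.0% vs 14.5% | 4.50 | 0.76 |
| 20% vs 10% | 0 | 20.0% vs 10.0% | 10.0 | 0.50 |
| | 2% | 21.6% vs 11.8% | 9.8 | 0.55 |
| | 5% | 24.0% vs 14.5% | 9.5 | 0.60 |
| | 10% | 28.0% vs 19.0% | 9.0 | 0.68 |

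The same holds for harm. With 20% on drug and 10% on placebo, the ratio of 2.00 falls to 1.83, 1.66 and 1.47 at q = 2%, 5% and 10%.

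**Denominator.** The factor (1-q) compares the observed difference with the difference among patients free of the symptom at dosing. If pre-dose onsets are removed from the numerator but all dosed patients stay in the denominator, the risks become (1-q)p1 and (1-q)p0. The risk ratio is then restored, but the risk difference is still (1-q)(p1 - p0).

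**Share of follow-up.** The pre-dose window is 4 of 32 days (12.5%) when follow-up runs to Day 28, or 2 of 30 days (6.7%) if the gap is 2 days.

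**The case against.** The best defence is that little depends on this. Section 12.4.1 plans descriptive frequencies, with no test or risk ratio for safety. The risk difference hardly moves: 5.00 to 4.75 points at q = 5%. That q has no source, and a 2-day gap would leave less time for pre-dose onsets. Section 12 leaves full methodology to a SAP. All of this limits the size of the point. It does not remove it, because the reference to screening is written into the endpoint and is not a detail left open. The Day 1 eligibility review does not remove it either: the exclusions in Section 7.2 catch severe disease, likely hospitalization and acute illness unrelated to COVID-19, not an additional mild COVID-19 symptom.

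Three stronger readings are tempting, and the documents do not support them.

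- **Pre-dose adverse events are attributed to the arms.** Section 10.1.3.2 takes AEs occurring "after the subject signs the informed consent form and up to the final follow-up visit", and Section 12.4.1 sets no onset filter. But Section 10.1.3.2 governs reporting and the database, not tabulation. The AE row of Table 1 is empty at screening and starts on Day 1. Section 10.1.2 classes events before first administration as unrelated. The Day 1 eligibility review and the need for a dose to enter the Safety population keep many affected patients out of the tables. A treatment-emergent rule is ordinary content for the SAP that Section 12 promises. This is missing detail, not a stated error.
- **Time of maximum severity can be negative.** A new symptom is absent at screening, no symptom record is scheduled between screening and Day 1, and the diary starts on Day 1. Its first scheduled severity record is therefore Day 1.
- **A quarter of the observation time is pre-dose.** That takes 4 of 16 days by stopping at Day 12, whereas the diary and AE collection continue to Day 28.

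**Conclusion.** The concern holds for the new-symptom endpoint. As written, a symptom that starts between screening and first dose is counted as an on-study event. The result is dilution and added noise, with no systematic advantage to either arm.

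Its size cannot be derived from the documents. Over assumed pre-dose rates of 2% to 5% and after-dose rates of 10% versus 5%, the risk ratio moves from 0.50 to between 0.58 and 0.67, and the risk difference falls by 2% to 5% of its value. These figures assume equal q in both arms and independence of pre-dose and after-dose onset. The classing of pre-dose AEs as unrelated gives this endpoint no evident protection, because the synopsis says clinical signs of COVID-19 are not reported as AEs.

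This is a minor, inexpensive improvement. The primary endpoint, its power and the secondary endpoints are untouched.

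**What to change.** Define a new COVID-19 symptom as one absent both at screening and at the Day 1 pre-dose assessment already in Table 1. If no Day 1 entry is shown to precede the dose, use screening alone. Have the Day 1 entry completed or time-stamped before dosing. State the denominator, preferably patients free of the symptom at that baseline. Reconcile the 4-day, 2-day and 48-hour descriptions of the gap.

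As a companion step, base by-arm AE tables on onset or worsening after first dose, list pre-dose AEs separately, and align the start of AE collection in Table 1 with Section 10.1.3.2.

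The cost is small: no extra visit or patients are needed. The endpoint wording changes in the synopsis and Section 5.2, and the analysis wording in the synopsis, Section 12.4.1 and the SAP. Because an endpoint definition changes, the allowance in Section 12 for changing statistical methods without an amendment may not cover it. Patients starting at home receive drug, diary and devices on the same day, so some Day 1 entries may not be verifiably pre-dose. Using a post-dose entry as baseline would hide early after-dose onsets, which is why the fallback to screening is needed.

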6 STUDY DESIGN

6.1 Study Description

This study is a phase 2, multiple-dose, double-blind, placebo-controlled, study to assess the safety and efficacy of TQ in patients with mild to moderate COVID-19. Approximately 275 patients with COVID-19 will be enrolled with the goal of reaching 250 patients meeting the criteria for the mITT population at the end of the study (~125 TQ, ~125 placebo).

After signing the informed consent form, patients will have medical history taken and undergo laboratory testing including G6PD, FDA-authorized RT-PCR from nasopharyngeal [NP] swab specimens) to confirm presence or absence of SARS-CoV-2, pregnancy testing, hematology, blood chemistry, vital signs, O₂ saturation, physical exams, and will be assessed for COVID 19 symptoms including presence/severity of cough, presence/severity of shortness of breath, oral or skin temperature, and respiration rate. Patients who are eligible to participate in the study will be randomized in a 1:1 ratio to TQ or placebo within 2 days of the screening visit and will receive treatment on Day 1. Patients not meeting eligibility criteria will be considered a screen failure. Rescreening is permitted if first SARS-CoV-2 RT-PCR is negative, provided the patient has not been symptomatic for five days when the first dose of study medication is administered.

On Day 1, eligible patients will either return to the clinic or may have a telemedicine visit. Continued eligibility will be reviewed, and if still eligible, patients will be randomized and will receive and self-administer 200 mg TQ or matching placebo on Days 1, 2, 3, and 10 (each administration of drug will be within \pm 1 day with the exception of the first dose). If the Day 1 visit is a telemedicine visit, the randomized blinded study drug will be couriered to the patient. Patients will be provided an oral thermometer to check and record their daily temperature and a home pulse oximeter to record their daily oxygen saturation. Patients will also be provided with an electronic study diary (eDiary) (loaded onto a device of their choosing) and be required to complete the eDiary entries from Day 1 through Day 12 [\pm 1 day]. Patients will record respiration rate, temperature, COVID-19 clinical signs including presence and severity of cough, respiration rate and shortness of breath, AEs, and concomitant medications in the electronic diary daily. They will also record study drug administrations in the diary to monitor compliance. Daily diary data will be automatically uploaded to the electronic data management system and will be reviewed daily by clinical staff.

Patients will be contacted by telephone or videoconferencing by designated study personnel on a daily basis to review AEs for severity by asking an open ended question, check for use of concomitant medications, and if there are new or worsening signs and symptoms of COVID-19 disease from Day 1 through Day 11 [\pm 1 day]. Telemedicine interviews will follow a script and information will be recorded in source documents. If a suspected SAE or worsening of signs and symptoms of COVID-19 are reported, a study physician will be contacted to determine if the patient needs additional support (clinic visit, medication, or emergency room visit). If the patient cannot be reached an individual from their emergency contact list will be contacted to determine if the patient has been hospitalized. Patients will return to clinic on Day 12 [\pm 1 day] for the assessments listed in [Table 1](#). From Day 13 [\pm 1 day] through Day 28 [\pm 1 day], patients will be instructed to complete the eDiary and will have a final telemedicine call on Day 28 [\pm 1 day].

The schedule of study procedures is illustrated in [Table 1](#).

6.1.1 Study Duration Per Patient

The total duration of the study will be up to 33 days for each patient, including 4 days for screening on Days -4 to -1, self-administration of study drug on Days 1, 2, 3, and 10, daily recording and remote collection of signs and symptoms from Day 1 through Day 11, an in-clinic visit on Day 12, and a telemedicine call on Day 28 ± day to assess AEs and clinical recovery.

6.1.2 Planned Number of Sites and Patients

The study will be conducted at multiple locations in the USA, Australia, or elsewhere as appropriate. Each site must have the capacity to conduct point of care COVID-19 RT-PCR test from NP swabs with a turn-around time no more than 48 hours. Sites must have access to point of care G6PD testing or be able to receive G6PD test result from an in-house or commercial laboratory within 48 hours. Sites must have pharmacy with capability to dispense study medication in secondary child-proof containers with appropriate labelling.

Approximately 275 patients with COVID-19 will be enrolled with the goal of reaching 250 patients meeting the mITT criteria at the end of the study.

6.1.3 Randomization

Eligible patients will be randomized at 1:1 ratio to receive TQ or placebo and stratified by site. Randomization will be performed through a centralized, web-based, validated system that automates the assignment of patients to treatment assignment. The randomization scheme will be reviewed and approved by the sponsor or designee. For study medication dispensation, the Investigator or designee will access the randomization system to determine which blinded study medication bottle the patients will be assigned.

6.2 Schedule of Study Assessments

Table 1 Schedule of Procedures

Procedure	Screening Day -4 to -1	Day 1	Day 1	Days 2 and 3 ± 1 day	Days 4 to 9	Day 10 ± 1 day	Day 11	Day 12 ± 1 day	Day 28 ± 1 day
Clinic Visit #	1	If in clinic	If at home					2 or 3	
Informed consent	X								
Eligibility criteria	X	X	X						
Pregnancy testing ¹	X							X	
Demography	X								
Medical history	X	updated	updated						
G6PD test	X								
Physical exam	X							X	
Vital signs ²	X							X	
Clinical symptoms of COVID-19 ³									
Temperature ⁴	X	X	Self-measured by patient daily and recorded in eDiary					X	
Respiration rate ⁵	X	X	Self-measured by patient daily and recorded in eDiary						
Shortness of breath (severity scale) ⁶	X	X	Self-reported by patient daily and recorded in eDiary					X	
Cough (severity scale) ⁷	X	X	Self-reported by patient daily and recorded in eDiary					X	
Pulse oximetry for oxygen saturation	X	X	Self-measured by patient daily and recorded in eDiary					X	
Prior and concomitant medications ⁸	X	updated	Recorded by clinician at telemedicine visit					X	Recorded by clinician at telemedicine visit
Adverse events			Self-reported by patient and recorded in eDiary, and recorded during telemedicine visit including severity and relationship to study drug, plus actions taken to treat AE or if drug discontinued					X	Recorded by clinician at telemedicine visit

Procedure	Screening Day -4 to -1	Day 1	Day 1	Days 2 and 3 ± 1 day	Days 4 to 9	Day 10 ± 1 day	Day 11	Day 12 ± 1 day	Day 28 ± 1 day
Clinic Visit #	1	If in clinic	If at home					2 or 3	
RT-PCR	X							X	
Hematology ⁹	X							X	
Blood chemistry ¹⁰	X							X	
Randomization		X	X						
Load eDiary to Patient Device, provide pulse ox device, thermometer, and instructions for use		X	X						
Dispense study drug ¹¹		X	X						
Study drug administration			X	Each day		X			
Medication compliance			eDiary	eDiary		eDiary			
Final drug accountability								X	

¹ A serum pregnancy test will be performed at screening and a urine or serum pregnancy test will be performed at Day 12.

² Vital signs include blood pressure and heart rate

³ COVID-19 symptoms will be assessed by designated clinical staff at in-clinic visits and will be checked at home by the patients and reported by the patient in the electronic diary (eDiary). Once the data is recorded in the diary it will be uploaded to the study database for clinician review.

⁴ Temperatures will be taken orally or on the skin surface and recorded in degrees Centigrade.

⁵ After resting for 3 minutes the number of breaths will be taken over one minute.

⁶ The severity of shortness of breath will be reported by the patient using the Modified Borg Scale for Grading the Severity of Dyspnea shown in [Section 15.2.1](#).

⁷ The severity of coughing will be reported by the patient using the Cough Severity Scale shown in [Section 15.2.2](#).

⁸ Prior medications used in the 14 days prior to the start of screening will be recorded.

⁹ Hematology tests include: WBC count, absolute neutrophil count, RBC count hematocrit, hemoglobin, platelet count; C-reactive protein, INR, PT/PTT.

¹⁰ Clinical chemistry tests include: BUN, creatinine, ALT and AST.

¹¹ Study drug will either be dispensed in the clinic, if the patient has a clinic visit on Day 1, or will be delivered by same day courier service to the patient at home on Day 1, after final eligibility has been determined the patient is randomized.

